#### 5. Premature Discontinuation of Investigational Agent

Study therapy may be prematurely discontinued for any participant for any of the following reasons:

- Occurrence of an AE that, in the opinion of the investigator, requires the participant's permanent withdrawal from the study agent. In the event of withdrawal from the study agent due to the occurrence of a SAE, the Investigator and Sponsor must be notified within 24 hours (See section 11.7). A participant withdrawn secondary to an ongoing SAE that is considered possibly or probably related to the study agent must be followed clinically until resolution or stabilization of the SAE.
- Insufficient therapeutic effect requiring alternative or additional therapy for the treatment of EoE, including the need for "rescue" systemic or swallowed inhaled corticosteroid therapy, in addition to the study agent, for the treatment of the current EoE. Criteria for withdrawal due to lack of efficacy will rely on the best clinical judgment of the PI that the participant requires a new therapeutic intervention due to the clinical state of his/her EoE. Examples would include: worsening of the presenting predominant symptom of EoE, the emergence of a new additional symptom of EoE that is at least moderate in intensity and is due to EoE, or the need for new systemic treatment (e.g., oral corticosteroids). In contrast, small dietary modifications or modest increases in symptom frequency without increased severity would not constitute withdrawal criteria.
- Study therapy may also be prematurely discontinued for any participant if the investigator believes that the study treatment is no longer in the best interest of the participant.

## 7 Other Medications

### 7.1 Concomitant Medications

Prior medications, such as acid reflux therapies (including PPIs with or without histamine H2 receptor antagonists) or swallowed corticosteroids (e.g. swallowed fluticasone), may be continued as concomitant medications during the study provided that the dose of the medication remains unchanged during the study period.

### 7.2 Table 3: Prohibited medications and washout time

Medication	Washout Time Prior to Screening Visit (i.e., Study Entry)
Anti-immunoglobulin E (IgE) mAb	6 months
Methotrexate, cyclosporine, interferon $\alpha$	3 months
Anti-tumor necrosis factor (TNF) mAb	6 months
Other systemic immunosuppressive or immunomodulatory agents	3 months
Angiotensin receptor blocker (ARB)	3 months
Angiotensin-converting enzyme inhibitor (ACEI)	3 months
Beta blocker (BB) therapy	3 months
Calcium-channel blocker	3 months
Other investigational drugs	3 months
Omalizumab	6 months
Anti-IL-5 agents	6 months
Anti-IL-13 agents	6 months
Other investigational drugs or device	1 month

Note: Any changes to the participant's asthma or allergy therapies and other concomitant medications during the study will be documented in the appropriate source documents and case report forms (CRFs).

### 7.3 Rescue Medications

No specific rescue medications are planned for this study

## 8 Study Procedures

### 1. Visit 1 Screening/ Baseline Visit (Week -12 to 0)

#### Recruitment

The research study will be explained in lay terms to each potential research participant. Participants will be recruited from the gastroenterology, allergy, or other clinics at each study site when potential participants with EoE and CTD may be seen. Participants who receive care from other institutions that express interest in participating may be enrolled in the study. The PI and the study staff team will work with the participant's primary care physician to explain the study objectives and requirements for the study. If the participant's primary care physician agrees that the participant would be a good candidate for the study, study staff will contact the participant and carry out all recruitment and screening procedures. In addition, potential participants will be identified through the EGD database (CCHMC IRB studies #2008-0090 and 2008-0098), as well as other databases and resources at each study site. Research staff will pre-screen or identify potentially eligible participants by conducting a review of existing medical and/or research records and IRB-approved recruitment materials.

The clinical trial information will be entered into a databank on [www.clinicaltrials.gov](http://www.clinicaltrials.gov) maintained by the U.S. National Library of Medicine (NLM) at the National Institutes of Health (NIH) or other websites.

The purpose of the screening period is to confirm eligibility to participate in the study. The screening visit should occur at a maximum of 12 weeks prior to the enrollment visit. The research staff member will perform the informed consent process according to Section 19. After obtaining informed consent, the following study assessments/procedures should be performed and documented up to 12 weeks prior to the enrollment (Week 0) visit or during the enrollment visit:

- Eligibility (inclusion and exclusion criteria)
- Medical, surgical and diet history
- Conduct vitals (blood pressure, heart rate, respiratory rate, temperature), height, and weight
  - Demographics (age, gender, race)
  - Physical exam performed by a study clinician
  - Clinical laboratory samples, including CBC with differential, chemistry, and IgE
  - Research laboratory samples (See Table 4)
  - Urine pregnancy test for females of childbearing potential
  - Concomitant medications and therapies
  - For those patients who meet the base screening inclusion/exclusion criteria, patients will be considered for evaluation of esophageal compliance via the use of EndoFLIP. EndoFLIP is a SOCEvaluation for esophageal dysmotility, done at the same time as their endoscopy. Patients will undergo consent to retrieve EndoFLIP datasets obtained prior to entry and during this study to assess esophageal compliance.

Note: If the participant is on a current dose of acid reflux therapy (e.g., PPIs and histamine H2 receptor antagonists) or swallowed corticosteroid (e.g. swallowed fluticasone), the participant is permitted to continue the acid reflux therapy or swallowed corticosteroid as long as the dose of the medication remains the same throughout the study. If the participant has had an EGD and biopsies performed at CCHMC or at an outside institution prior to the screening visit, the results of the EGD may be used to determine eligibility if it falls within the 12-week window prior to enrollment. These participants will have all other screening procedures completed at the in-office, screening visit. EGDs performed at an outside institution may be used as baseline if the corresponding pathology report and slides are available and reviewed by the CCHMC research pathologist to determine eligibility. In addition, EoE Endoscopic Reference Score (EREF) will be obtained endoscopies performed at the participating institutions.

Some participants who have been seen at CCHMC or at other institutions may have had research samples, tissue and blood, collected at the time of their EGD for further analysis to occur in the [REDACTED] or in the [REDACTED]. If so, permission to utilize the participants' samples for this study will be obtained at the time of informed consent, and will be transferred to the respective labs under a material transfer agreement. Screening physicals will be performed by trained physicians using the Villefranche criteria, Beighton, and Ghent criteria (79, 80). These are simply guidelines, and a physician can still have the capability to provide a participant with a diagnosis of a CTD if their scores do not fall within the abnormal limits.

## 8.2 Visit 2 Enrollment / Titration Cycle 1 / (Week 0)

All eligible participants will be enrolled into the study at Week 0 if they meet all eligibility criteria and have completed the screening procedures. Screening and enrollment visits may be combined when deemed necessary. If the screening and enrollment visit are combined, the study drug will not be dispensed until all inclusion and exclusion criteria have been met and all screening visit procedures have been performed. This includes the review of all laboratory tests performed during the screening portion of the visit. If a participant is screened and enrolled within a 5-day time frame, study procedures that would be repeated will only be performed once. The enrollment visit also marks the beginning of the Treatment Phase and Titration Cycle 1. At this visit, staff members will:

- Reassess eligibility (inclusion and exclusion criteria)
- Conduct vitals (blood pressure, heart rate, respiratory rate, temperature), height, and weight
- Administer patient- and parent-reported outcome questionnaires
- Urine pregnancy test in females of childbearing potential
- Assess and inquire about AEs
- Assess concomitant medications and/or therapies
- Assess participant compliance with diet
- Dispense study agent with instructions

- Dispense diet and medication log

The PI or the sub-investigator will determine the initial dose of study agent per the titration schedule in Sections [6.1.2 - 0](#). The participant's weight obtained at this visit will be used to calculate the initial dose of losartan. The Investigational Pharmacy will dispense the appropriate dose and amount of the study agent per the Manual of Operations (MOO). The participant will be instructed to administer the study agent orally once daily, at approximately the same time each day, with or without food, for at least 21 days but less than 28 days. The participant will also be instructed to record the start and stop date of the study agent and each dose in the study diary. The participants will be instructed to call the PI and/or study coordinator if they have any questions, concerns, adverse events, or changes in medication.

### 8.3 Telephone Calls (Week 1)

On Days 6, 7, or 8 of Titration Cycles 1 (Week 1) after the start of the titrated doses, the study coordinator will call the participant for the following purposes:

- Verify the absence of ADRs
- Verify the absence of AEs
- Inquire about changes to concomitant medications/therapies and diet
- To answer any participant's questions and concerns

ADRs and changes to concomitant medications should be recorded in the participant's source documents. If the participant experiences ADRs, the PI should be consulted, and the appropriate procedures should be followed to adjust the study agent administration and down-titration, as needed and at the discretion of the PI (See sections [6.1.2 - 0](#)).

### 8.4 Visit 3 Up-titration / Titration Cycle 2 / (Week 4)

Up-titration (beginning of maintenance Phase; Week 4) will be conducted in the clinic. The study visit should occur after the participant has taken the study agent for at least 21 days but less than 28 days (7-day window). The following study procedures should be performed:

- Conduct vitals (blood pressure, heart rate, respiratory rate), height, and weight
- Physical exam
- Administer patient- and parent-reported outcome questionnaires
- Clinical laboratory samples, including CBC with differential, chemistry
- Urine pregnancy test in females of childbearing potential
- Assess AEs
- Assess changes to concomitant medication/therapies (to ensure participant has not taken any prohibited medication)

- Assess participant compliance with diet (to ensure no diet change)
- Sample / Diary Collection
  - Collect diet and medication log
    - Collect study agent bottle and unused study agent
- Medication accountability
  - Determine participant's compliance with study agent during Titration Cycle 1
- Dispense
  - Dispense study agent with instructions
  - Dispense diet and medication log

The participant's weight obtained at this visit will be used to determine the study agent dose for Titration Cycle 2. Up-titration should only occur if the participant has verified the absence of ADRs. The maximum tolerated dose for the study agent will not exceed 100 mg per day. The dose will be determined at this visit (Week 4) and will continue throughout the maintenance phase.

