### 3. Reducing Risks of Losartan Use

To minimize the potential risks of losartan, the starting doses of the study agent will be relatively low and will be up-titrated carefully (See section [6.1.2](#)). Participants will be followed closely for adverse drug reactions (ADRs) and will only be up-titrated if the current study agent dose is tolerated. In addition, clinical labs (i.e., complete blood count [CBC] with differential and chemistry) will be measured to monitor serum creatinine, potassium, hemoglobin, hematocrit, AST, and ALT; any abnormalities in laboratory values that are determined to be AEs will be evaluated and managed by the Investigator.

Pregnancy or planned pregnancy during the trial is exclusionary as losartan exposure represents a high-risk problem for the fetus if a mother is inadvertently exposed to losartan during pregnancy. The use of losartan would not merit potential benefit in EoE, given the significant risk of frank mortality and morbidity to the fetus associated with these exposures. At the time of informed consent and throughout the study, female participants of childbearing potential and their legal guardians will be educated and notified about the potential risk of the study agent. The risk will also be described in the consent and the assent forms. Birth control measures will be required for female participants of childbearing potential.

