Of note, in review of patients enrolled into the CCHMCEGID research database, 5% of all EoE patients have a weight which exceeds 90 kg. When limited to those EoE patients who are 18 and older, this percentage climbs to 8%. This indicates that the pool of patients is small and only a few patients would be at risk for the maximum dose planned for this clinical trial at the outset of their enrollment. Review of blood pressures for 6 subjects enrolled in the trial to date reveals that the lowest systolic and diastolic blood pressure percentiles were 27th and 21st percentile respectively following initiation of losartan.

The participants will be instructed to call the study coordinator or the study physician if any Adverse Drug Reactions (ADRs) occur. On day 6, 7, or 8, after each dosing visit, the study coordinator will contact each participant (or parent/legal guardian) and verify the absence of ADRs.

After each participant has taken the study agent for at least 21 days but less than 28 days (7-day window), they will return to the clinic for a visit. During that visit the research staff will verify the absence of ADRs. If no reported ADRs the participants will then proceed to Cycle 2 (see below).

#### Up-titration: Titration Cycle 2

Up-titration will proceed according to the schedule outlined in Table 2. The dose of study agent will be increased as tolerated to a dose of approximately ~1.4 mg/kg, not to exceed 100 mg. The maximum dose will continue through the maintenance phase. For each cycle, after participants have taken the agent for at least 21 days but less than 28 days (7-day window), the study coordinator will verify the absence of ADRs.

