## 4. Toxicity Prevention and Management

If a participant develops certain ADRs such as fatigue or dizziness, the study agent can be changed to night-time administration or twice-a-day administration at the discretion of the PI. If drug reactions persist or abnormalities are noted in the safety lab work, the dose of the study agent will be decreased by the down-titration increments listed in Table 2. The participant will be withdrawn from the study if serum creatinine, serum potassium, AST, or ALT are increased such that they would be classified as a moderate or more severe AE according to the schema in the Common Terminology Criteria for AEs (CTCAE) (77). For serum creatinine, this value is greater than 1.5 times the upper limits of the age-matched normal value; for potassium, this value is 5.6-6.0 mEq/L in a non-hemolyzed sample; and for AST and ALT, this value is greater than 2.5 times the upper limit of the age-matched normal value. Abnormal laboratory values for serum creatinine, serum potassium, AST, and ALT will always be measured twice to re-examine for error.

If the participant's blood pressure (systolic and diastolic) falls below the 2nd percentile for age listed in the study staff-generated guideline report for blood pressure ranges for children and adolescents (See section 19) and has concurrent symptoms of hypotension, the participant's dosage will be decreased by the down-titration increments listed in Table 2. If the participant is asymptomatic, this will not be considered hypotension. Participants will be re-evaluated after down-titration of the study agent at the PI's discretion. Unlike the situation with heart-rhythm abnormalities associated with withdrawal of beta-blockers (78), there is no similar literature noted for ARB medications and no taper of losartan is planned following completion of the study.

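### Sections 8.4 and 6.1.2 let the higher cycle 2 dose start before the Visit 3 chemistry, the first scheduled on drug, has been reviewed

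*Protocol*

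**What the plan says.** Section 8.4 puts three steps into one clinic visit. Staff take "Clinical laboratory samples, including CBC with differential, chemistry"; they set the cycle 2 dose from that day's weight; and they dispense it. The dose is then fixed: "The dose will be determined at this visit (Week 4) and will continue throughout the maintenance phase". The cycle 1 bottle and any unused drug are collected at the same visit.

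The conditions for the increase are these:

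- Section 8.4: "Up-titration should only occur if the participant has verified the absence of ADRs".
- Section 6.1.2: a participant with no reported ADRs goes on to cycle 2, and "The dose of study agent will be increased as tolerated to a dose of approximately ~1.4 mg/kg, not to exceed 100 mg".
- Section 5.3: participants "will only be up-titrated if the current study agent dose is tolerated". Laboratory monitoring follows as a separate statement: "any abnormalities in laboratory values that are determined to be AEs will be evaluated and managed by the Investigator".

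Section 6.4 says what laboratory findings lead to: "If drug reactions persist or abnormalities are noted in the safety lab work, the dose of the study agent will be decreased". It also requires withdrawal for creatinine above 1.5 times, or AST or ALT above 2.5 times, the age-matched upper limit, and for potassium of 5.6-6.0 mEq/L. Abnormal values of these four are to be measured twice.

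Table 4 marks clinical laboratory samples at Screening and at Weeks 4, 8, 12 and 16.

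**The concern.** The trial has one planned dose increase and one scheduled on-drug laboratory check before or at that increase, but nothing links the two. A rise in potassium, creatinine or transaminases need not cause symptoms, so a participant's report of no ADRs does not stand in for the result. Followed as written, the plan can raise the dose of someone whose sample, drawn the same day, will call for a reduction or withdrawal under Section 6.4. At stake is a short, avoidable period at a higher dose in a trial that enrols from age 5. The efficacy analysis is not affected.

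**Working it through.** This is mainly a comparison of sections; the arithmetic only sizes the gap. The plan gives no figure of its own on this point to reproduce.

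**1. Is Visit 3 the first on-drug chemistry?** Yes, among scheduled samples. Table 4 has none at Week 0, Week 1 or Week 5.

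**2. Could the ADR or tolerability condition cover the result?** Not reliably. In Section 8.4 the participant verifies the absence of ADRs, and cannot verify a value drawn that day. Section 6.4 names drug reactions and laboratory abnormalities as alternatives, so it treats them as different things. Even if a laboratory abnormality is read as an ADR, the Visit 3 value is unknown when the drug is dispensed unless the laboratory reports the same day.

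**3. What chemistry is known at the increase?** The screening sample, taken off drug. Section 8.1 allows it from 12 weeks before enrollment up to the enrollment visit. Cycle 1 lasts 21 to 28 days.

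- Shortest age: 0 weeks + 21 days = 3 weeks.
- Longest age: 12 weeks + 28 days = 16 weeks.

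**4. How large is the step?** Inputs are Table 2 (cycle 1: 0.7-0.9 mg/kg; cycle 2: 1-1.4 mg/kg, maximum 100 mg) and Section 6.1.2 (adults start at 50 mg), with weight *w* in kg.

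Under 18, ratio = min(cycle 2 mg/kg × *w*, 100) / min(cycle 1 mg/kg × *w*, 100):

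- Up to 100/1.4 = 71.4 kg: 1.0/0.9 = 1.11 to 1.4/0.7 = 2.0.
- At 90 kg: 90/81 = 1.11 to 100/63 = 1.59.
- From 100/0.9 = 111 kg, at 0.9 mg/kg in cycle 1: 100/100 = 1.0, no increase.

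Adults, applying the Table 2 range, ratio = min(cycle 2 mg/kg × *w*, 100) / 50:

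- 50 kg: 50/50 = 1.0 to 70/50 = 1.4.
- 60 kg: 60/50 = 1.2 to 84/50 = 1.68.
- 71.4 kg: 71.4/50 = 1.43 to 100/50 = 2.0.
- 100 kg or more: 100/50 = 2.0.

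**5. How long is the exposure?** Turnaround is not in the documents. At an assumed 1 to 3 days with once-daily dosing, 1 to 3 higher doses are taken before the result is known. It could be more if the site waits for the repeat measurement before acting.

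**6. How often would it happen?** The documents give no usable rate for this population. Section 5.2 reports minor BUN or creatinine rises in under 0.1% of patients with essential hypertension on losartan alone, and one discontinuation (under 0.1%) for liver tests. If 0.1% is assumed for each of 15 participants, the chance of at least one is 1 − 0.999^15 = 1.5%. That illustrates the creatinine/BUN figure only. The documents give no rate for a potassium rise in patients without renal disease.

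**The case against.** The strongest reply is that the gap is real on paper but matters little. Section 5.1 reports no dose-related adverse event frequency over 10 to 150 mg in the hypertension trials. Section 6.1.2 cites pediatric use up to 2.5 mg/kg/day, against about 1.4 here. Raised creatinine, hepatic insufficiency, ACE inhibitor or ARB use and potassium supplements are all excluded (Section 4.3, criteria 5, 7, 12 and 14). The one severe hyperkalemia case described in Section 1.5 had pre-existing renal insufficiency and concurrent ACE inhibitor use. Visit 3 includes vital signs and a physical exam, and Section 6.4 acts once a result is in. A site with same-day results could review them first, and the Manual of Operations or Pharmacy Manual may already require it. All of this stands as to size. It does not supply the missing condition in the protocol.

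Three stronger readings are tempting, and the documents do not support them:

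- A reader might infer that Section 8.4 contradicts Section 8.2, which withholds drug at a combined screening and enrollment visit until laboratory tests are reviewed. That is an eligibility check before the first dose, not a titration rule. Nor does 8.4 contradict 6.4, which governs action after an abnormality is noted.
- A reader might infer from the Week 5 call in Section 8.5, which does not list laboratory review, that the results go unread. It is a coordinator's checklist; Section 5.3 gives laboratory abnormalities to the investigator.
- A reader might infer a sizeable chance of an affected participant from the pediatric proteinuria studies in Section 1.5. That population differs, and in the randomized study reduced GFR was no more of a problem than on amlodipine/placebo and losartan was not stopped.

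**Conclusion.** The point holds as a minor, low-frequency safety sequencing gap. As written, absence of ADRs and a tolerated dose are enough for the increase, and the Visit 3 chemistry need not be seen first. The result can be a dose step of up to 2.0-fold in a participant who already meets a Section 6.4 reduction or withdrawal limit, with the last known chemistry 3 to 16 weeks old and off drug.

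Expected harm is small: the event is probably uncommon and the exposure is likely a few doses. Both statements rest on assumptions about turnaround and event rate. The conclusion covers the protocol and SAP only; an equivalent step in either manual would close the gap in practice. It is worth correcting because the remedy is simple.

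**What to change.** Add to Sections 8.4 and 6.1.2:

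*The first cycle 2 dose is taken only after the investigator has reviewed the Visit 3 creatinine, potassium, AST and ALT and found no abnormality requiring dose reduction or withdrawal under Section 6.4. Until then the participant continues the cycle 1 dose and starts cycle 2 on telephone instruction. If a value must be repeated under Section 6.4, the hold lasts until the repeat is reviewed.*

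No separate supply is needed, because the cycle 1 dose can be taken from the drug dispensed at Visit 3. The suspension is the same 2.5 mg/mL: for a 30 kg child, cycle 1 is 21/2.5 = 8.4 mL to 27/2.5 = 10.8 mL, and cycle 2 is 30/2.5 = 12 mL to 42/2.5 = 16.8 mL. Tablets come as 25 mg and 50 mg; an adult takes one 50 mg tablet in cycle 1.

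State also that the hold does not breach the 28-day limit in Section 8.4, Table 2 and Table 4 footnote b. With a 3-day hold, a Visit 3 by day 24 still ends cycle 1 by day 24 + 3 = 27; later visits need the allowance.

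Costs:

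- About 15 telephone calls, one per participant.
- A short delay to cycle 2. An assumed 1 to 3 days is 1/84 = 1.2% to 3/84 = 3.6% of the 12-week (84-day) maintenance phase, and longer if a repeat is needed.
- A small dosing-error risk from giving two dose instructions at one visit, which the call and clear labelling limit.
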